**Resistance:**

For all subjects receiving study drugs in Part 1, and subjects with available samples in Part 2 of the study, the polymorphisms at signature resistance-associated amino acid positions at baseline identified by next generation sequencing (NGS) and comparison to the appropriate prototypic reference sequence will be analyzed.

The following resistance information will be analyzed for all subjects receiving study drug who do not achieve SVR12 and who have a post-baseline sample with HCV RNA  $\geq$  1000 IU/mL: 1) the amino acid substitutions in available post-baseline samples identified by NGS and comparison to the baseline sequences, 2) the amino acid substitutions in available post baseline samples at signature resistance-associated positions identified by NGS, and comparison to the appropriate prototypic reference sequence, and 3) the persistence of viral resistance by NGS.

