### **GLE/PIB Dose Selection Strategy for the Pediatric Population**

AbbVie's pediatric formulation development strategy is to develop a dosage form that provides suitable and flexible dosing across the pediatric age range of 3 to < 18 years. Development of a suitable pediatric formulation was guided by considerations of solubility, dose flexibility, stability, compatibility, and ease and reliability of the manufacturing process. It is likely the adult tablets will be suitable for adolescent subjects 12 years of age and older with weights  $\geq 45$  kg. This population is able to swallow tablets and utilizing the adult tablet would enable earlier enrollment of this population. In Part 1 of Study M16-123, a total of 47 adolescent subjects received daily administration of GLE/PIB 300 mg/120 mg. PK results showed that the exposures of GLE and PIB in HCV-infected adolescent subjects (12 to < 18 years of age) were similar to the exposures observed in HCV-infected adult subjects following administration of GLE/PIB 300 mg/120 mg.

GLE and PIB exhibit low aqueous solubility. Due to probable requirement of solvent(s) that are undesirable for pediatric patients for any oral solution, and [REDACTED]

[REDACTED] AbbVie developed a pediatric formulation based on the solid oral formulations used to manufacture the adult tablets.

[REDACTED]

To provide exposures in pediatric subjects comparable to adult exposures using the pediatric formulation, the GLE and PIB dose in pediatric patients of 3 to < 12 years of age were revised from originally proposed doses. Preliminary PK results from the initial

proposed pediatric doses demonstrated that though GLE and PIB exposures were within the range of exposure for efficacy and safety in adults for each of the pediatric cohorts, the average exposures in each of the cohorts were lower than the targeted AUC and led to a dose adjustment. Additional subjects were enrolled and the intensive PK results obtained, and additional population PK modeling performed, confirming that the adjusted doses demonstrate exposures that would allow for bridging of adult data, using a 50/20 mg dose ratio. These doses (Table 11) are proposed to be used in the subjects enrolling in the non-IPK portion of Part 2, in order to confirm that the doses would provide similar exposures observed in HCV-infected adult subjects, close to the targeted AUC.

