## **5.0 Investigational Plan**

### **5.1 Overall Study Design and Plan: Description**

The study is designed to enroll approximately 125 subjects to meet scientific, regulatory and clinical objectives without enrolling an undue number of subjects in alignment with ethical considerations. Therefore, if the target number of subjects has been enrolled, there is a possibility that additional subjects in screening will not be enrolled. All subjects must undergo a mandatory Fibrosis Assessment prior to enrollment into Part 1 or Part 2 of the study (refer to Section 5.3.1.1 for more details).

Part 1 of the study allows for enrollment of approximately 44 HCV infected, GT1 – 6 pediatric subjects into the 12 to < 18 years old age group who weigh  $\geq 45$  kg and are able to swallow (whole tablets – without crushing or breaking) the adult formulation of GLE/PIB. Part 2 of the study allows for enrollment of approximately 81 HCV infected, GT1 – 6 pediatric subjects divided into the 3 to < 6, 6 to < 9 and 9 to < 12 years old age groups. Subjects will receive the pediatric formulation of GLE/PIB in Part 2.

[figure not shown]
Each age group in Part 1 and Part 2 will enroll approximately 12 HCV infected subjects to adequately characterize the pharmacokinetics of a particular age group. Those individuals will undergo an intensive PK sample draw at the Week 2 visit with blood samples taken immediately prior to dose (0 hour) and at 2, 4, 6, and 12 hours post dose. After the approximately first six (6) subjects per age cohort complete the intensive PK at the Week 2 visit, the PK samples of those subjects will be analyzed to determine dose adjustments of GLE/PIB in an age cohort, if needed. After the intensive PK analysis results are available, enrollment will resume with approximately six (6) additional subjects per age cohort and intensive PK of all approximately twelve (12) subjects will be evaluated to determine if the study drug doses have achieved therapeutic exposures which have been demonstrated to be safe and efficacious in adult subjects. Additional subjects may be required for further intensive PK analysis per age cohort if therapeutic exposure targets have not been achieved. Once doses have been confirmed based on intensive PK data for a respective age group, enrollment into the safety/efficacy portion of that age group may begin.

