### **8.1.6 Resistance Analysis**

#### **8.1.6.1 HCV Drug-Resistance Analyses**

The secondary endpoint of resistance associated viral variants will be analyzed as follows. For all subjects in Part 1 and subjects with available samples in Part 2, full length NS3/4A or NS5A from baseline samples will be sequenced by NGS. For all subjects who experience virologic failure (on-treatment virologic failure or post-treatment relapse), full length NS3/4A and NS5A genes from the first sample after virologic failure with HCV RNA  $\geq 1000$  IU/mL will be sequenced by NGS. An appropriate subtype-specific prototypic reference sequence will be used for comparison with sequences from samples. Subjects treated with study drug who do not achieve SVR12 due to reasons other than virologic failure but have a time point with HCV RNA  $\geq 1000$  IU/mL after treatment discontinuation, will have the sample at that time point sequenced.

Only samples with an HCV RNA level of  $\geq 1000$  IU/mL will undergo sequence analysis in order to allow accurate assessment of products of amplification. Therefore, if the HCV RNA level at the time of HCV virologic failure or treatment discontinuation is  $< 1000$  IU/mL, the sample closest in time after HCV virologic failure/treatment discontinuation with an HCV RNA level  $\geq 1000$  IU/mL will be used. Included time

points for analyses on samples from subjects who do not achieve SVR12 are 1) the sample closest in time after failure/discontinuation with an HCV RNA level of  $\geq 1000$  IU/mL, and 2) 24 weeks post-DAA treatment, provided that resistance-associated substitutions were detected by NGS at the time of HCV virologic failure/treatment discontinuation.

For each DAA target, signature amino acid positions and a key subset of amino acid positions are listed in [Table 12](#). Appropriate subtype specific prototypic reference sequence will be used for comparison with sequences from samples.

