- A by subject listing of baseline polymorphisms (15% detection threshold) at signature amino acid positions in subjects with polymorphisms across both NS3 and NS5A, or those with multiple baseline polymorphisms within any one target (NS3/4A or NS5A).
- The number and percentage of subjects with baseline polymorphisms at signature amino acid positions at detection thresholds of 2% and 15%.
- Total number and percentage of subjects with baseline polymorphisms at a key subset of amino acid positions in NS3 only, in NS5A only, any in NS3, any in NS5A, any in NS3 or NS5A, any in NS3 + NS5A, by subtype, and total (include all subtypes).

**Analysis 2:** The impact of baseline polymorphisms on treatment outcome will be assessed as follows: for each polymorphism, the SVR12 rate will be calculated for subjects with and without the polymorphism and the 2 rates will be compared using Fisher's exact test. Analysis will be grouped by HCV subtype and DAA target (NS3/4A or NS5A).

The following will be included in the analyses of impact of baseline polymorphisms on treatment outcome:

- For each signature amino acid position, presence of any polymorphism at that position (vs no polymorphism at that position), using detection thresholds of both 2% and 15%.
- Each individual polymorphism at each signature amino acid position (vs not that polymorphism) using detection thresholds of 2% and 15%.
- Polymorphisms at each non-signature amino acid position at a detection threshold of 15%.

**Analysis 3:** In subjects with or without polymorphisms in NS3 only, in NS5A only, any in NS3, any in NS5A, any in NS3 or NS5A, any in NS3 + NS5A at the key subset of amino acid positions at 15% detection threshold, the SVR12 rate will be calculated, and the rates with or without polymorphisms will be compared using Fisher's exact test. Analysis will be separated by HCV subtype. The following tables will be provided:

- Comparison of SVR12 rates by subtype, and total (include all subtypes)
- Comparison of SVR12 rates by genotype, and total (include all subtypes)

**Analysis 4:** The following analyses will be performed for subjects who do not achieve SVR12 and who have post-baseline resistance data available:

- Listings by subject of all treatment-emergent substitutions relative to the baseline amino acid sequences will be provided for each DAA target (NS3/4A and NS5A).

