- The number and percentage of subjects with baseline polymorphisms at detection-thresholds of 2% and 15% at signature amino acid positions (ITT). This table includes prevalence of each baseline polymorphism, and a summary of the number of subjects with polymorphisms in NS3 only, NS5A only, any in NS3, any in NS5A, any in NS3 or NS5A, and any in NS3 + NS5A.
- Total number and percentage of subjects with baseline polymorphisms *at the key subset of amino acid positions* in NS3 only, NS5A only, any in NS3, any in NS5A, any in NS3 or NS5A, and any in NS3 + NS5A (ITT), by subtype, and total.
- Total number and percentage of subjects with baseline polymorphisms *at the key subset of amino acid positions* in NS3 only, NS5A only, any in NS3, any in NS5A, any in NS3 or NS5A, and any in NS3 + NS5A (ITT), by genotype, and total.

Analysis 2: Analysis 2 will be applicable to Cohort 1 only. The impact of baseline polymorphisms on treatment outcome will be assessed for the **mITT-VF** population as follows: for each polymorphism, the SVR₁₂ rate will be calculated for subjects with and without the polymorphism and the two rates will be compared using Fisher's exact test. Analysis will be grouped by HCV genotype/subtype and DAA target (NS3 or NS5A).

The analysis will include the number of subjects within each genotype/subtype with variants in NS3 only, NS5A only, any in NS3, any in NS5A, any in NS3 or NS5A, and any in NS3 + NS5A.

The following will be included in the analyses of impact of baseline polymorphisms on treatment outcome:

- Polymorphisms at signature amino acid positions (vs no polymorphism at that position), using detection thresholds of both 2% and 15%. The analysis will include the number of subjects with polymorphisms in NS3 only, in NS5A only, any in NS3, any in NS5A, any in NS3 or NS5A, and any in NS3 + NS5A.
- Each polymorphism at signature amino acid position (vs not that polymorphism) using detection thresholds of 2% and 15%. The analysis will include the number of subjects with polymorphisms in NS3 only, in NS5A only, any in NS3, any in NS5A, any in NS3 or NS5A, and any in NS3 + NS5A.

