Analysis 3: Analysis 3 will be applicable to Cohort 1 only. In subjects with or without baseline polymorphisms in NS3 only, in NS5A only, any in NS3, any in NS5A, any in NS3 or NS5A, and any in NS3 + NS5A at the *key subset of amino acid positions* at 15% detection threshold, the SVR₁₂ rate will be calculated, and the rates with or without polymorphisms will be compared using Fisher's exact test. Analysis will be separated by HCV subtype. The following tables will be provided (mITT-VF):

- Comparison of SVR₁₂ rates by subtype, and total (including all subtypes)
- Comparison of SVR₁₂ rates by genotype, and total (including all genotypes)

Analysis 4:

The following analyses will be performed for subjects who do not achieve SVR₁₂ (with separate summaries for subjects in PVF and non-PVF populations) and have post-baseline resistance data available:

- Listings by subject of all *treatment-emergent variants* relative to the baseline amino acid sequences will be provided for each DAA target (NS3/4A and NS5A).
- Listings by subject of all *variants at signature amino acid positions* in a post-baseline time point for each DAA target (NS3 and NS5A).
- The persistence of post-baseline variants at signature resistance-associated amino acid positions for each target (NS3 and NS5A) from subjects will be assessed at Post-Treatment Week 24. Listings by subject and time point of all treatment-emergent variants will be provided for each DAA target (NS3 and NS5A).

HCV Genotype/Subtype

Phylogenetic analysis will be conducted on HCV sequence from baseline samples for all subjects in Part 1, and from subjects with available sample in Part 2 in order to accurately determine subtype.

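### SAP 10.8.1 limits the SVR12-by-baseline-polymorphism comparisons to Cohort 1, while the current protocol plans them for every subject with baseline sequence, including Part 2.

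*SAP*

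**What the plan says.** **Protocol 8.1.6.1** sets who is sequenced at baseline: "For all subjects in Part 1 and subjects with available samples in Part 2, full length NS3/4A or NS5A from baseline samples" are to be sequenced by NGS. The synopsis describes the same group. For Part 2, the study procedures section takes the Day 1 resistance sample only where it fits the allowable blood volume. In Analysis 2, the SVR12 "rate will be calculated for subjects with and without the polymorphism and the 2 rates will be compared using Fisher's exact test". Analysis 3 makes the same kind of comparison at the key subset of positions. Neither carries a cohort restriction.

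**SAP 10.8.1** also sequences every available baseline sample. It then states "Analysis 2 will be applicable to Cohort 1 only" and "Analysis 3 will be applicable to Cohort 1 only", places both in the mITT-VF population, and gives no reason for the limit. Just before Analysis 1, it also has the resistance analyses run cohort by cohort. The SAP does not say what Cohort 1 is. In the protocol synopsis it is the group aged 12 to <18 years and at least 45 kg, which is Part 1.

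**Sizes (protocol).** Section 5.1: "Part 1 of the study allows for enrollment of approximately 44 HCV infected, GT1 – 6 pediatric subjects" and "Part 2 of the study allows for enrollment of approximately 81 HCV infected, GT1 – 6 pediatric subjects". The dose-selection text in the Introduction reports that "a total of 47 adolescent subjects received daily administration of GLE/PIB 300 mg/120 mg" in Part 1.

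**The concern.** The two documents give different populations for the same comparison, and the narrower one leaves out data that both documents plan to generate. Under the SAP, no child on the pediatric formulation contributes to an SVR12 rate with or without a polymorphism.

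The adult data leave at least one such question open. For GT3, the protocol Introduction lists the NS5A positions that did not affect outcome, and position 30 is not among them. It also reports A30K at both baseline and post-treatment in 9 of the 18 GT3 failures analysed.

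Virologic failure is rare with this regimen, and mITT-VF drops non-responders whose reason was not virologic failure. If no virologic failure occurs in the analysed set, every table reads 100% against 100% and every Fisher p-value is 1. A smaller analysed set makes that more likely.

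**Working it through.** The documents give no sample size or power for these analyses, so there is no stated figure to reproduce. The enrolment figures agree with each other: 44 + 81 = 125.

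**Failure rate (assumed equal to adults).** The Introduction reports 23 virologic failures in treatment-naïve and PRS-experienced adults, one of them a re-infection. SAP 10.8.1 groups re-infection with the non-virologic reasons for non-response, so 22 apply. Table 3 gives 2,206 SVR12 responders of 2,256. The mITT-VF-type rate is 22/(2,206 + 22) = 22/2,228 = 0.99%.

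**Analysed numbers.** Cohort 1: 47 treated (44 planned). Half of Part 2 sequenced: 44 + 40.5, about 85. All sequenced: 44 + 81 = 125, or 47 + 81 = 128. The share of Part 2 with a sample is not stated, so half to all is shown as a range.

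**Formulas.** With p = 0.00987: expected failures = np; P(none) = (1 − p)^n; P(two or more) = 1 − (1 − p)^n − np(1 − p)^(n−1).

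| n | Expected failures | P(none) | P(two or more) |
|---|---|---|---|
| 44 | 0.43 | 0.65 | 0.07 |
| 47 | 0.46 | 0.63 | 0.08 |
| 85 | 0.84 | 0.43 | 0.21 |
| 125 | 1.23 | 0.29 | 0.35 |
| 128 | 1.26 | 0.28 | 0.36 |

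**Sensitivity of the n = 47 result to the rate.**
- No GT3: 4/(1,594 + 4) = 0.25%, P(none) = 0.89.
- All GT3: 18/(612 + 18) = 2.86%, P(none) = 0.26.
- Twice the overall adult rate: P(none) = 0.39.
- P(none) equals one half at 1 − 0.5^(1/47) = 1.46% (1.56% for n = 44).

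**What one failure can show.** If the single failure carries the polymorphism and m of n subjects carry it (m below n/2), the two-sided Fisher p-value is m/n. At n = 47, 2/47 = 0.043 and 3/47 = 0.064, so p < 0.05 needs at most 2 carriers. With the adult GT1 NS5A carrier share of 26.8%, about 13 of 47, p = 13/47 = 0.28. At n = 125 the limit is 6 carriers (6/125 = 0.048).

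**Power, by enumeration (illustrative effects, 26.8% carriers, two-sided 0.05).**
- Failure 3% in carriers and 0.3% in others, an overall rate of 0.268 × 3% + 0.732 × 0.3% = 1.0%, close to the adult rate: power 0.01 at n = 47 and 0.08 at n = 125.
- Failure 10% and 0.3%, an overall rate of 2.9%, about three times the adult rate: 0.15 and 0.64.

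Splitting by subtype, as both documents plan, lowers these further.

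**The case against.** **Part 2 sequences are not discarded.** A reader might infer that they are never related to outcome. SAP 10.8.1 does not support that. Analysis 1 covers all subjects, and its listings show each subject's reason for SVR12 non-response next to the baseline polymorphisms. Analysis 4 covers non-responders with post-baseline data in any cohort, and the sequences also feed subtyping. With about one failure expected, such a listing may tell more than a Fisher test. This stands; what is missing is the SVR12 rate with and without the polymorphism.

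**An undeclared change is not shown.** SAP 12.1 does not list the limit among its changes from the protocol, which might suggest an omission. But the SAP elaborates the amendment dated 25 July 2017, which is not supplied, and the section numbers cited in 12.1 differ from those of the 2019 protocol. Whether the earlier text held the same limit is unknown. The SAP also planned about 110 subjects; at n = 110, P(none) would be 0.34.

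**These are not shown to be the children in whom polymorphisms matter most.** Average exposure at the initial Part 2 doses was below target, which makes that reading tempting. The same text says exposures lay within the adult range for efficacy and safety, and the Introduction reports no effect of baseline polymorphisms on SVR12 in adult GT1, 2, 4, 5 or 6.

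**Rare failure, more than the limit, makes the tables empty.** This is largely right. With all-cause non-response (50/2,256 = 2.2%), P(none) at n = 47 would be 0.35, so mITT-VF contributes too.

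**The limit may be deliberate.** Part 1 is the only part sampled in full by design, and restricting to it is defensible. The SAP would then need to say so.

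**Conclusion.** The concern holds as a mismatch between the SAP and the current protocol. SVR12 by baseline polymorphism is computed for Cohort 1 only, the term is undefined in the SAP, no reason is given, and children under 12 have no such rate although their available samples are sequenced. The number affected is at most about 81 and depends on blood-volume limits.

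At the adult failure rate, aligning the two documents lowers the chance of an empty comparison from about 63% to between 43% (half of Part 2 sequenced) and 28–29% (all sequenced). These figures assume that the adult rate carries over to children. Protocol 3.2 allows that pediatric failure may be higher, and above about 1.5% an empty Cohort 1 result is no longer the more likely outcome. The case for the change is consistency with the protocol and use of data already in hand; it does not give the tests useful power.

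**What to change.** In SAP 10.8.1, replace both Cohort 1 restrictions with: *all mITT-VF subjects with baseline sequence for the target*. Amend the sentence before Analysis 1 that has the work done cohort by cohort, so that Analyses 2 and 3 show Part 1, Part 2 and combined results; without this, lifting the restriction would still give no combined table. Footnote that Part 2 sequences are a convenience subset determined by blood-volume limits.

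If the limit is intended, the minimum is to define Cohort 1 in the SAP and state the reason for departing from protocol 8.1.6.1.

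The cost is three SAP sentences, a footnote and a further run of table programs already needed for Cohort 1. No new samples or sequencing are required. The one small downside is the selected nature of the Part 2 subset, which the footnote and the separate columns make visible.

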**Resistance:**

The polymorphisms at signature resistance-associated amino acid positions at baseline will be tabulated and summarized for all subjects receiving study drugs in Part 1. For subjects in Part 2 of the study, baseline polymorphisms will be determined based on availability of samples. For all subjects who experience virologic failure and have an HCV RNA  $\geq 1000$  IU/mL, post-baseline substitutions relative to the baseline sequence and to the appropriate prototypic reference sequence will be tabulated and summarized.

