SVR₁₂ = HCV RNA $<$ LLOQ in the SVR₁₂ window (12 weeks after the last actual dose of study drug) without any confirmed quantifiable (\geq LLOQ) post-treatment value before or during that SVR window.

SVR₂₄ = HCV RNA $<$ LLOQ in the SVR₂₄ window (24 weeks after the last actual dose of study drug) without any confirmed quantifiable (\geq LLOQ) post-treatment value before or during that SVR window.

Relapse₁₂ = confirmed HCV RNA \geq LLOQ between end of treatment and 12 weeks after last actual dose of active study drug (up to and including the SVR₁₂ window) for a subject with HCV RNA $<$ LLOQ at Final Treatment Visit who completed treatment excluding reinfection as described below.

Relapse₂₄ = confirmed HCV RNA \geq LLOQ within the SVR₂₄ window for a subject who achieved SVR₁₂ and has HCV RNA data available in the SVR₂₄ window, excluding reinfection.

Relapse_{overall} = confirmed HCV RNA \geq LLOQ between end of treatment and up to and including the last HCV RNA measurement collected in the PT Period for a subject with HCV RNA $<$ LLOQ at Final Treatment Visit who completed treatment excluding reinfection.

Virologic failure = On-treatment virologic failure or Relapse_{overall}.

Only subjects who have at least one post-treatment HCV RNA value will be included in analyses of relapse. For the analysis of relapse, completion of treatment is defined as a study drug duration of 52 days or greater for subjects assigned to 8 weeks of treatment, 77 days or greater for subjects assigned to 12 weeks of treatment, and 103 days or greater for subjects assigned to 16 weeks of treatment. If the last available post-treatment value is \geq LLOQ, then the subject will be considered a relapse (i.e., will not require confirmation).

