10.8 Resistance Analyses

10.8.1 HCV Drug-Resistance Analyses

Full length NS3/4A or NS5A from all available baseline samples will be sequenced by next generation sequencing (NGS). For subjects who experience virologic failure (on-treatment virologic failure or post-treatment relapse as defined in Section 10.1), full length NS3/4A and NS5A genes from the first available sample after virologic failure with HCV RNA ≥ 1000 IU/mL will be sequenced by NGS. An appropriate subtype specific prototypic reference sequence will be used for comparison with sequences from samples. Subjects who experience virologic failure will be referred to as subjects in the primary virologic failure (PVF) population, and a listing by subject that includes HCV genotype/subtype, IL28B genotype, reason for SVR₁₂ non-response, time point(s) sequenced as closest to time of VF, and HCV RNA value at the VF time point(s) will be produced for these subjects. In addition, all listings described below will display HCV genotype/subtype and reason for SVR₁₂ non-response in the subject identifier for each subject. A separate listing will summarize all subjects in the PVF population for whom no sequencing was performed (e.g., lost to follow-up while HCV RNA ≤ 1000 IU/mL).

Subjects treated with study drug who do not achieve SVR₁₂ due to reasons other than virologic failure (prematurely discontinued study drug with no on-treatment virologic failure, HCV reinfection, missing SVR₁₂ data or other reasons as described in Section 10.1, Reasons for SVR₁₂ Non-Response), but have a time point with HCV RNA ≥ 1000 IU/mL after treatment discontinuation, will have the sample at that time point sequenced. These subjects will be referred to as the non-PVF population. A listing of all subjects in the non-PVF population with post-baseline sequencing available will be created that is similar to the listing of subjects in the PVF population with post-baseline sequencing available.

For each DAA target, signature amino acid positions and a key subset of amino acid positions are listed in Table 14. Appropriate subtype-specific prototypic reference sequence will be used for comparison with sequences from samples.

Table 14. List of Genotype-Specific Signature Amino Acid Positions and Key Subsets of Amino Acid Positions

Genotype	Signature Amino Acid Positions	Key Subset of Amino Acid Positions
NS3/4A		
1a	36, 43, 54, 55, 56, 80, 107, 122, 132, 155, 156, 158, 168, and 170	155, 156, 168

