1b	36, 54, 55, 56, 80, 107, 122, 155, 156, 158, 168, 170, and 175	155, 156, 168
2, 3, 4, 5, 6, 1 – other (non 1a/1b)	36, 43, 54, 55, 56, 80, 155, 156, 166 (GT3 only) and 168	155, 156, 168
NS5A		
1a	24, 28, 29, 30, 31, 32, 58, 62, 92, and 93	24, 28, 30, 31, 58, 92, 93
1b	24, 28, 29, 30, 31, 32, 54, 58, 62, 92, and 93	24, 28, 30, 31, 58, 92, 93
2, 3, 4, 5, 6, 1 – other (non 1a/1b)	24, 28, 29, 30, 31, 32, 58, 92, and 93	24, 28, 30, 31, 58, 92, 93

Included time points for analyses on samples from subjects who do not achieve SVR₁₂ are 1) the sample closest in time after failure/discontinuation with an HCV RNA level of ≥ 1000 IU/mL, and 2) 24 weeks post-DAA treatment, provided that resistance-associated variants were detected at the time of failure/discontinuation.

The following definitions will be used in the resistance analyses:

- Baseline polymorphism: a polymorphism by NGS in a baseline sample ($\geq 2\%$ or $\geq 15\%$ prevalence within a subject's viral population depending on frequency threshold utilized) that was not present in the appropriate prototypic reference amino acid sequence for a given DAA target (NS3/4A or NS5A)
- Variant at signature amino acid position: variant (relative to reference) present by NGS at a detection threshold of 2% or 15% (depending on frequency threshold utilized) in a baseline or a post-baseline sample at a signature amino acid position
- Post-baseline variant: an amino acid variant in a post-baseline time point sample that was not detected at baseline ($< 2\%$) in the subject and is detectable in $\geq 2\%$ of the sequences from the post-baseline sample

- Enriched variant: variant present in both the baseline and a post-baseline sample whose prevalence in the post-baseline sample is at least 20 percentage points greater than the prevalence in the baseline sample [(post-baseline % – baseline %) ≥ 20]
- Treatment-emergent variant by NGS: A post-baseline variant or an enriched variant

Analysis will be performed separately for each cohort by HCV genotype/subtype within each listing.

Analysis 1: The following analyses will be performed for all subjects:

- A listing of all baseline polymorphisms (2% detection threshold) at signature amino acid positions for each DAA target (NS3 and NS5A) (ITT).

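### SAP 10.8.1 sequences relapse after SVR12 as virologic failure, but Analysis 4 lists post-baseline substitutions only for subjects who do not achieve SVR12

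*SAP*

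**What the plan says.** **Definitions (SAP 10.1).** Virologic failure is on-treatment failure or overall relapse. Overall relapse is a confirmed quantifiable value found "between end of treatment and up to and including the last HCV RNA measurement collected in the PT Period". The subject must have completed treatment and been below the LLOQ at the Final Treatment Visit, and reinfection is excluded. Failure to achieve SVR12 is not required. The SAP clearly foresees failure after SVR12, since Relapse24 is defined "for a subject who achieved SVR₁₂ and has HCV RNA data available in the SVR₂₄ window".

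**Sequencing and populations (SAP 10.8.1).** NS3/4A and NS5A are sequenced from the first available sample after virologic failure with HCV RNA of at least 1000 IU/mL. "Subjects who experience virologic failure will be referred to as subjects in the primary virologic failure (PVF) population". The non-PVF population consists of subjects without SVR12 for reasons other than virologic failure.

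**Analysis (SAP 10.8.1).** The time-point sentence begins "Included time points for analyses on samples from subjects who do not achieve SVR₁₂ are" and names the sample closest after failure or discontinuation, and 24 weeks post-treatment. Analysis 4 begins "The following analyses will be performed for subjects who do not achieve SVR₁₂ (with separate summaries for subjects in PVF and non-PVF populations". It requires post-baseline resistance data, and it assesses persistence at Post-Treatment Week 24.

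**Protocol.** The synopsis, under criteria for evaluation, has post-baseline substitutions tabulated "For all subjects who experience virologic failure and have an HCV RNA" of at least 1000 IU/mL. Section 8.1.6.1 follows persistence through Post-Treatment Week 144. Other protocol text uses the narrower SVR12 non-achiever population: the synopsis statistical methods for resistance, Section 5.3.4, and in Section 8.1.6.1 both the included time points and Analysis 4.

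**The concern.** The SAP builds a failure population that includes late relapse, and then restricts the analysis of that population by a criterion late relapsers do not meet. The mention of separate PVF and non-PVF summaries does not repair this, because it divides the SVR12 non-achievers and does not add to them.

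Emergence and persistence of viral variants in subjects with available samples is a secondary objective (Protocol 4.2, SAP 4.1), with no SVR12 condition attached. The synopsis gives durability of SVR12 as one reason for the 144-week follow-up, and Protocol 8.1.2.3 lists relapse after SVR12 as an additional efficacy endpoint. If a late relapse occurs, the plan gives no rule for presenting its post-baseline sequence. That choice would then be made after the case is known.

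**Working it through.** The plan states no figure to reproduce. The check is a cross-reading of the SAP, followed by arithmetic on the visit windows and a rough size.

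**1. Classify a test case.** Take a child who completes treatment (at least 52, 77 or 103 days for 8, 12 or 16 weeks) and is below the LLOQ at the Final Treatment Visit and in the SVR12 window. The child first has a confirmed quantifiable value at Post-Treatment Week 48 and is not reinfected.

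- SVR12 (SAP 10.1): achieved.
- Relapse12: no. Relapse24: no, because the value lies outside that window.
- Overall relapse: yes, and so virologic failure: yes.
- Sequenced: yes, if HCV RNA reaches 1000 IU/mL.
- PVF: yes. Non-PVF: no, because that population also requires SVR12 not achieved.

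**2. Trace the child through the SAP outputs.**

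| Output | Child included? | Post-baseline substitutions shown? |
|---|---|---|
| PVF listing (10.8.1) | Yes | No; genotype, IL28B, sequenced time point, HCV RNA |
| Relapse summary by window (10.7) | Yes | No |
| Analysis 1 | Yes, if baseline sequence exists | No; baseline polymorphisms |
| Analyses 2 and 3 (Cohort 1 only) | As an SVR12 responder | No; baseline polymorphisms |
| Analysis 4 | No | This is the only output that would show them |

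**3. A second gap.** A child who stops treatment early, reaches SVR12 and then relapses fails the completed-treatment condition, so is not a virologic failure and not in PVF. Having achieved SVR12, the child is not in non-PVF either. SAP 10.7 lists early discontinuers who relapse, but Analysis 4 does not reach this child.

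**4. Window arithmetic (SAP Table 4).** The SVR12 window is Days 57 to 126 and the Week 144 visit is nominal Day 1,008.

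- Planned follow-up after the SVR12 window: 1,008 − 126 = 882 days; 882 / 1,008 = 87.5%.
- Scheduled HCV RNA visits after it: Weeks 24, 36, 48, 96 and 144, which is 5 of 7.
- The Week 24 window closes on Day 210. A relapse first seen at Week 36 (Day 252) or later could not be assessed for persistence at Week 24, even if Analysis 4 were widened.

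**5. Size.** Protocol Section 3.0 reports 23 adult virologic failures among treatment-naïve and TE-PRS subjects. One was a reinfection, leaving 22 analysed. Table 3 gives 2,256 such subjects, 2,206 with SVR12.

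- 22 / 2,256 = 0.98%; × 125 = about 1.2 failures expected here, if the adult rate carries over.
- Expected SVR12 responders: 125 × 2,206 / 2,256 = about 122.
- The documents give no late-relapse rate. Over an assumed range of 0 to 1%, 122 × 0 to 0.01 gives 0 to 1.2 children.

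**The case against.** The strongest reply is that SAP Analysis 4 follows the protocol. Protocol 8.1.6.1 limits its own Analysis 4 and included time points to SVR12 non-achievers, and Section 5.3.4 and the synopsis statistical methods do the same. The broader synopsis sentence need not cover late relapse, because the secondary relapse endpoint in Protocol 8.1.2.2 stops 12 weeks after the last dose. This stands. A reader might infer that the SAP contradicts the protocol on the population, but the documents do not support that. The protocol is mixed, and the firm conflict is between the SAP's own definition of virologic failure and its own Analysis 4. The SAP also elaborates a July 2017 amendment, whereas the supplied protocol synopsis is dated March 2019, so some differences may be version drift.

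A reader might also infer that resistance in late relapsers goes entirely unreported. It does not, since baseline polymorphisms, the sequenced time point and HCV RNA are all reported. Only the post-baseline substitution and persistence listings are missing. The field for the SVR12 non-response reason would be blank for these children, but that is no fault in itself. It is equally blank for every SVR12 responder in the Analysis 1 listings.

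A third tempting inference is that up to half of all failures would be lost: 1.2 / (1.2 + 1.2). That figure depends wholly on taking the top of an assumed range, and the bottom of the range is zero.

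Finally, Analysis 4 consists of descriptive listings by subject. No SVR12 rate, relapse count or confidence interval depends on it. That is correct and limits the weight of the point, but does not remove the gap.

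**Conclusion.** The point holds as an inconsistency within the SAP. A late relapser who completed treatment and was not reinfected is counted as a virologic failure and sequenced when HCV RNA allows. The same subject is then outside the only analysis of treatment-emergent variants, post-baseline variants at signature positions and persistence. No other SAP output supplies these.

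The period exposed to the gap is 87.5% of planned follow-up, but the number of children affected is unknown, probably very small and possibly zero. The estimate of about 1.2 failures assumes that adult rates apply, and the range of 0 to 1.2 late relapsers is an assumption, not a finding from the documents. No primary result changes. The reason to correct it is that failures will be few, each sequence is informative for a secondary objective, and the rule should be set before a case appears.

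**What to change.** In SAP 10.8.1, define Analysis 4 and the included time points as covering, wherever post-baseline sequence data exist:

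- all PVF subjects, stating that this includes relapse after SVR12;
- all non-PVF subjects;
- any subject who discontinued treatment early and relapses after SVR12.

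Label the late rows *relapse after SVR12* in place of the SVR12 non-response reason. For these subjects use the first sample after relapse with HCV RNA of at least 1000 IU/mL, plus later available samples. Replace the single Week 24 persistence assessment with assessment through Post-Treatment Week 144, as in the persistence paragraph of Protocol 8.1.6.1. The protocol's own time-point sentence, which names only 24 weeks, should be reconciled with that paragraph.

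The sponsor should also confirm that the samples will exist. Protocol Appendix C draws post-treatment resistance samples only from those who meet virologic failure criteria, and the criteria in Section 5.4.1.1 are all on-treatment.

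The cost is mainly SAP wording and a few extra listing rows. Some later samples may also need sequencing, and a short protocol clarification may be needed on when the samples are drawn.
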